The participant is asked to allow MRI scans to be stored and used for research at a later time. Participants that refuse to have scans kept for future research will be excluded from the study. The MRI scans will be stored indefinitely. The scans may be given to other investigators or MRI technology companies for future research as well. The future research may take place at Pennington Biomedical and may involve Pennington Biomedical Researchers in this study. The MRI scans may be shared with faculty at the LSU School of Kinesiology. The future research may not take place at Pennington Biomedical Research Center and may not be reviewed by Pennington Biomedical Research Center's Institutional Review Board. For privacy and confidentiality, MRI scans will be labeled with a unique series of letters and numbers. Pennington Biomedical will store MRI scans with this unique identifier. The research done with MRI data may help to develop new products in the future, or may be used to establish a diagnostic test that could be patented or licensed. The participant will not receive any financial compensation for any patents, inventions or licenses developed from this research.

References:

1. Mattes RD. Dietary compensation by humans for supplemental energy provided as ethanol or carbohydrate in fluids. *Physiol Behav.* 1996;59(1):179-187.
5. Saris WHM. Limits of human endurance: lessons from the Tour de France. . In: Kinney JM, Tucker HN, eds. *Physiology, stress, and malnutrition: functional correlates, nutritional intervention.* . Philadelphia: Lippincott-Raven Publishers; 1997:451-462.

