Protocol Title: The Diet composition and Energy Balance Pilot Study (The DEB Pilot Study)

PI: [name]

Co-PI: [name]

Sub-Investigators:

[name]

[name]

[name]

Background:

Food form refers to the physical state of foods, i.e., if food is in beverage (liquid) or solid form. Adults do not fully compensate for calories consumed in beverages over the short-term in preload studies; therefore, it is thought that food form can affect energy intake and body weight^{1,2}. A meta-analysis of pre-load studies by Almon-Roig suggested that food form affects energy intake³. However, previously it has been shown that energy compensation typically takes 2-6 days in humans; thus, the validity of preload studies has been questioned^{4,5}. Over four weeks, there is a weight gain with carbohydrate beverage intake but no difference between carbohydrate beverage and solid food form treatments². In another four-week study, participants who consumed sugar-sweetened beverages (SSBs) gained far less weight than expected should no compensation have occurred⁶ and in a commentary on the article it was noted that further research is needed to determine if people compensate differently over the long-term to energy consumed in solid vs. liquid form⁷. Similarly, others have called for additional research on the extent to which compensation occurs over the long-term in response to energy from SSBs⁸.

The effect of sugar intake on body weight over the long-term is not well understood when a liquid SSB and an SSB consumed in solid form are provided that are similar in macro- and micronutrients. Thus, the purpose of the current study is to test if weight change is differentially affected by consumption of foods that are identical in carbohydrate (i.e. sugar) but vary in food form over 1 month. There will be no instructions provided for any other dietary modifications.

The provided foods that will be consumed by participants daily for 1 month in this study are:

1) 1 20 oz. carbonated sugar sweetened beverage (SSB; 240 kcals). Added ingredients include: ~2.1g whey protein powder.

Or

2) 1 solid food that is made with the SSB syrup concentrate and is equivalent to one 20 oz. soft drink (solid; 240 kcals). Added ingredients: ~30 g water, ~3.0 g gelatin, ~3.5 mg sodium (added using NaCl), ~11.1 mg potassium (added using KCl) and ~11.5 mg calcium (added using CaCl).

Specific Aims:

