Aim 1. Test the feasibility of having participants consume liquid and solid foods for 1 month and demonstrate our ability to acquire and analyze fMRI brain activation pre and post dietary intervention with a visual reward paradigm.

Aim 2. Test for change in body weight.

Hypothesis: The SSB group will have no difference in change in body weight compared to the solid group (between group effects). The SSB and solid groups will have increased weight compared to baseline (within group effects).

Changes in brain activation will be measured and tested for differences among the groups. It is hypothesized that change in brain activity will not differ between the SSB and solid groups. But, it is hypothesized that both the SSB and solid group will experience change in activation in reward-related areas of the brain compared to baseline.

The foods listed above will be provided to participants with instructions to consume one serving per day. The energy content of food provision in the SSB and solid groups will be 240 kcal/day (SSB and solid groups will be isocaloric). Participants will receive no instructions for other dietary modifications; i.e., they will not be told to modify what or how much other food they consume.

Inclusion and Exclusion Criteria:

The target study group will be 20 men and women aged 21 to 65 years. 10 participants will be randomized to the SSB and solid groups, respectively. The participant population will include normal weight, overweight and obese (BMI 20.0 to 40.0 kg/m²) individuals. All inclusion/exclusion criteria will be based upon self-reported medical history/checklist. Participants must be able to consume study foods and be willing to archive their brain scans and eye tracking data. Participants who consume SSBs will be asked to maintain their regular SSB consumption in addition to the SSB (or solid food) associated with their random assignment). Participants will be stratified based on sex and BMI class.

Exclusion Criteria:

Health Conditions:

- Diabetes (Type 1 or 2)
- Prediabetes
- Active cancer
- Serious digestive disorders
- Other conditions that affect metabolism or body weight
- Uncontrolled Thyroid disorder (controlled = 6 months of medication)
- Unable to consume study foods
- Non- weight stable (more than 10 lbs. weight gain or loss in last 6 months)
- Pregnancy
- Intentions of becoming pregnant in the next 2 months
- Women who have undergone partial hysterectomy with intact ovary function

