The Advertising and Recruitment Cores are responsible for recruiting potential participants for clinical trials from a population that includes a wide range of people of various ages, ethnic backgrounds and with varying degrees of health. Pennington Biomedical has a team of full-time employees dedicated to the recruitment and initial screening of clinical trials. Potential subjects will be identified via a large database of previous study participants along with the use of web, print, and media advertising. The Recruitment and Advertising Cores create and implement individualized, trial-specific advertising and awareness campaigns, including mass media, traditional advertising, and novel methods including social media, digital and email marketing. All advertising and awareness are approved by our on-site IRB to ensure ethical and disclosure standards are met. The PBRC database will also be utilized to find potential subjects for this study.

Study Timelines

Participants will come in for a screening visit. Then approximately a week (~ 7 days) later, participants will come in their Week 0 (baseline) study visit and be provided with ~1 week (~7

days) of food provision. This visit will occur based on self-reported luteal phase of menstrual cycle in women. Next, at approximately 1 week (~day 7), participants will return to the center for an adherence visit and further provision of study foods (Week 1). At approximately 2 weeks (~day 14), participants will return to the center for an adherence visit and further provision of study foods (Week 2). At approximately 3 weeks (~day 21), participants will return to the center for an adherence visit and further provision of study foods (Week 3). Finally, participants will come for their Week 4 assessment and adherence visit. Thus, participation will last approximately 5-6 weeks in total.

Study Endpoints

Study Design: A randomized parallel arm design trial examining solid sugar vs. SSB treatments will be performed. The primary study endpoints are feasibility and change in body weight.

Procedures Involved

Overview:

Participants will arrive at the center following a minimum 10 hour fast. They will undergo anthropometric measurements, psychological and behavioral questionnaires, and fMRI.

Table 1. Schedule of Procedures

| Visit Assessments | Screening Visit | Intervention Period | | | | |
|--|-----------------|---------------------|--------|--------|--------|--------|

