Pulse oximeter: The pulse oximeter is an optical sensor that clips onto one of the fingers of either hand or toes of either foot. It shines a light through the skin to gather proxy measures of blood oxygenation while the scan is being collected. Dynamic MRI data, especially functional and perfusion MRI, is commonly corrected by regressing the time course of peripheral blood oxygenation out of the raw time series data acquired. The sensor attaches snugly to the finger but generally does not pinch or cut off the flow of blood.

Image and video display screen: Participants view images projected from a screen through a mirror mounted on the MRI head coil. Commonly deployed experimental paradigms display images during fMRI data collection to assess responses of the brain to various visual stimuli.

Headphones: MR-safe headphones are worn inside the head coil and over the ears.

Button boxes: In functional MRI experiments, participants are commonly asked to indicate responses to questions about the images, sounds, smells, and tastes exposed to them in the scanner by pressing buttons on button boxes placed in their hands.

MR scanning

The scanner technician runs a series of sequence acquisitions, each of which quantify a different aspect of tissue structure and function, or covers a slightly different portion of the anatomy. Each sequence acquisition emits a series of buzzing or grinding noises over the course of 1 to 10 minutes while data is acquired. Before each sequence acquisition, the technician communicates with the participant via a speaker and microphone inside the scanner bore; the participant is asked about his/her comfort and is reminded to lie perfectly still during the subsequent sequence acquisition. The technician has an unobstructed view of the participant to identify movement during acquisition or other signs of discomfort. After scanning, the participant is removed from the scanner tube and assisted out of the scanner suite.

Statistical analysis. The study will use an intent to treat approach. Following evaluation of data normality, a mixed model ANOVA will be used to test if change on the outcome variables differed between treatment and control across time. LS Means will also test if change from baseline was significantly different from 0. Fixed effects will include age and sex.

Power Analysis:

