Since this is a pilot and feasibility study, power calculations have not been performed. This study will allow us to obtain crucial feasibility data as well as data to perform future power calculations for a larger grant.

Data Banking

The PIs and co-investigators will have access to the data for future analysis and they may be shared with outside investigators.

Data Management

The data management will be conducted by the Pennington Biomedical Research Computing Group. There will be limited access to all data including locked cabinets for paper files and password protected computers for electronic data. Identifiers will be kept separate from the data.

Provisions to Monitor the Data to Ensure the Safety of Subjects

The Principal Investigators (PIs) are responsible for monitoring the data, assuring protocol compliance and conducting safety reviews at the specified frequency [quarterly]. During the review process, the Principal Investigators will evaluate whether the study should continue unchanged, requires modification/amendment or should close to enrollment.

The Principal Investigators or the Institutional Review Board (IRB) or have the authority to stop or suspend the study or require modifications.

This protocol presents minimal risks to subjects, and adverse events or other problems are not anticipated. In the unlikely event that such events occur, the PIs are responsible for reporting to the IRB and any appropriate funding and regulatory agencies any serious, unanticipated and related adverse events or unanticipated problems involving risks to subjects or others. The investigators will apprise fellow investigators and study personnel of all adverse events that occur during the conduct of this research project. The investigator will meet this obligation through email as they are reviewed by the Principal Investigators. The study's Research Monitor(s) and decision-making bodies will be informed of serious adverse events within 10 working days of the event becoming known to the Principal Investigators. If there are unanticipated problems involving risks to subjects or others, these should be reported to the IRB per HRPP Policy 8.0.

The sub-investigator, [name], will review adverse events.

Withdrawal of Subjects

Subjects may be withdrawn from the study if he/she misses study visits or food provision and will be notified of their withdrawal via telephone or mail.

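### The between-group hypotheses of no difference are the null of the only stated between-group test, which with 10 per arm could refute them but could not support them

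*Protocol*

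**What the plan says.** Specific Aims gives two between-group hypotheses. For weight: "The SSB group will have no difference in change in body weight compared to the solid group". For imaging: "It is hypothesized that change in brain activity will not differ between the SSB and solid groups". Separate hypotheses predict change from baseline within each arm.

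Study Endpoints gives weight its status: "The primary study endpoints are feasibility and change in body weight".

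Two passages describe the between-group analysis. Specific Aims says: "Changes in brain activation will be measured and tested for differences among the groups". Statistical analysis says that "a mixed model ANOVA will be used to test if change on the outcome variables differed between treatment and control across time". A further sentence there, "LS Means will also test if change from baseline was significantly different from 0", concerns change from baseline and so serves only the within-group hypotheses.

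Background gives a reason to expect no difference. It cites a four-week study that found "no difference between carbohydrate beverage and solid food form treatments". Power Analysis is candid about size: "Since this is a pilot and feasibility study, power calculations have not been performed". It adds that the data are meant for power calculations for a larger grant.

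**The concern.** The investigators' hypothesis is the null hypothesis of the test they plan. Failing to reject a null is not evidence for it unless the study could have detected a difference that matters. In a small trial the predicted result is easy to obtain whether or not the prediction is true.

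The protocol states no between-group estimate, interval or margin that would show how close the arms are. As written, the natural report of a non-significant result is that a hypothesis on a primary endpoint was borne out, when the data may be compatible with a sizeable difference in either direction. For planning the larger study, the useful outputs are the estimated difference, its interval and the SD of change.

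**Working it through.** **Inputs from the protocol.** 10 per arm (Inclusion and Exclusion Criteria); age and sex as fixed effects (Statistical analysis); 240 kcal/day (Specific Aims); about 4 weeks, taken as 28 days (Study Timelines). The protocol states no significance level, SD, effect size or margin, so it has no figure of its own to reproduce.

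**Assumptions.** Two-sided 0.05; all 20 participants analysed; one uncorrected contrast; SD means the residual SD of change. Residual df = 20 − 4 = 16 (intercept, arm, age, sex).

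**1. Precision in SD units.** 95% CI half-width = t(0.975, 16) × √(2/10) = 2.120 × 0.447 = 0.948 SD. Without covariates (18 df) it is 0.940 SD.

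**2. How often the predicted result occurs when the hypothesis is false.** Non-central t, 16 df, non-centrality d/√0.2:

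- d = 0.5 SD: P(non-significant) = 0.817
- d = 0.8 SD: P(non-significant) = 0.609
- 80% power is reached only at about 1.33 SD

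With 18 df the two probabilities are 0.815 and 0.605, so the covariates hardly matter.

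**3. How far a non-significant result separates the cases.** Under no difference its probability is 0.95. The ratios are 0.95/0.817 = 1.16 against 0.5 SD and 0.95/0.609 = 1.56 against 0.8 SD. Both are weak.

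**4. In kilograms, on assumptions not in the protocol.** Take 7,700 kcal per kg and an SD of 4-week weight change of 0.8, 1.0 or 1.5 kg. Then 240 × 28 / 7,700 = 0.873 kg. That is the gap if one arm compensates fully and the other not at all; half of it is 0.436 kg.

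| | SD 0.8 kg | SD 1.0 kg | SD 1.5 kg |
|---|---|---|---|
| 95% CI half-width (kg) | 0.76 | 0.95 | 1.42 |
| P(non-significant), true 0.436 kg | 0.791 | 0.849 | 0.906 |
| P(non-significant), true 0.873 kg | 0.370 | 0.550 | 0.768 |
| P(90% CI within ±0.873 kg), true difference 0 | 0.510 | 0.209 | 0.008 |
| Smallest n per arm for 80% success on the row above | 16 | 24 | 52 |

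The last two rows are by simulation, with df = 2n − 4. At SD 0.8 kg and a true 0.873 kg, the ratio from step 3 becomes 0.95/0.370 = 2.57, so in that case a non-significant result is moderately informative.

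**The case against.** The strongest reply is that nothing wrong is written down. Background gives the purpose as finding out whether food form affects weight change, and a difference test answers that question. The no-difference statement is then an expectation, grounded in an earlier four-week study, and a test that could contradict an expectation is coherent. The protocol never claims equivalence, sets no rule for reading p > 0.05 as equality, and says it is unpowered. The mixed model yields the difference and its interval as standard output, and a statistical analysis plan, not shown here, might specify them.

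Much of this stands. It makes the point a mismatch and not a contradiction, and the missing power calculation is not being faulted. Three limits on the figures also stand:

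- A non-significant result gives some weak support, as the ratios show.
- The kg figures rest on outside assumptions, and 0.87 kg is an extreme scenario.
- The SD-unit figures are for a single contrast, so they do not directly size the imaging hypothesis if several regions are tested.

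What does not stand is that pilot status or an unseen plan removes the problem. The protocol itself labels the statements hypotheses, attaches one to a primary endpoint, and pairs both with a difference test. Low power makes the predicted result easier to obtain, so the pilot label strengthens the case for not calling that result support.

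**Conclusion.** The concern holds. It is worth fixing and modest in size. The stated between-group analysis can refute the no-difference hypotheses, and even that reliably only for differences of about 1.33 SD or more. It cannot support them: the predicted non-significant result would also appear in about 82% of trials with a true 0.5 SD difference and 61% with 0.8 SD. These figures need no assumed SD or margin. They do rest on a two-sided 0.05 level, 10 analysed per arm and one contrast; dropout would make them worse. On the assumed weight SDs, an equivalence test at ±0.87 kg would be under-powered at 10 per arm throughout (51%, 21% and 0.8% success), though not impossible at the smallest SD. Estimation therefore suits this pilot better than a formal similarity claim.

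**What to change.** In Specific Aims (Aim 2) and Statistical analysis, state the between-group weight and brain-activation objectives as estimation. Suggested wording:

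> The SSB-minus-solid difference in change from baseline will be estimated from the mixed model, adjusted for age and sex, and reported with its 95% CI and the SD of change. A p-value above 0.05 will not be read as evidence of no difference, and no claim of similarity will be made from this pilot.

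The expectation of no difference can stay as background, resting on the four-week study already cited. Leave the within-group hypotheses as they are. Leave any equivalence test, with a justified margin, to the larger trial.

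The cost is wording plus one contrast. The contrast comes from the planned model but should be written in, because the LS Means sentence covers only change from baseline. No extra participants, visits or data are needed. The one downside is that the pilot can no longer be reported as confirming its between-group hypotheses.

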- Any uncorrected vision problems
- Color-blindness
- Left-handed
- Current or past alcohol or drug abuse problem

- Have internal metal medical devices including cardiac pacemakers, aortic or cerebral aneurysm clips, artificial heart valves, ferromagnetic implants, shrapnel, wire sutures, joint replacements, bone or joint pins/rods/screws/clips, metal plates, metal fragments in your eye, or non-removable metal jewelry such as rings.
- Other contraindications to magnetic resonance scanning
- Unable or unwilling to complete the imaging procedures for the duration of the MRI scan due to claustrophobia or other reason.
- Allergy or intolerance to study product ingredients.
- Any other medical, psychiatric or behavioral factors that in the judgment of the Principle Investigator that may interfere with study participation or the ability to follow the protocol

Medications/Non-Drug Therapies (within ~4 weeks prior to Screening):

- Weight loss medications, diet pills
- Non-topical steroids
- Other medications that may affect fluid balance or weight

Lifestyle:

- Consume more than seven 12 oz. sugar-sweetened beverages per week (~ 1, 12 oz. SSB/day; diet soft drinks are ok)
- Consume > 3 drinks/day of any alcoholic beverage
- Smoker. (Former smokers must be smoke free for 6 months)
- You plan to move out of the study area within the next 3 months, or plan to be out of the study area for more than 1 week (~7 days) during the course of the study.

Number of Subjects

We will enroll 20 right handed men and women aged 21-65 y with a BMI of 20.0-40.0 kg/m².

Recruitment Methods

Traditional PBRC recruiting methods will be utilized by marketing and the recruiting core.

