| | | Week 0 | Week 1 | Week 2 | Week 3 | Week 4 |
| Informed Consent | X | | | | | |
| Anthropometrics (height, body weight) | X | | | | | |
| Anthropometrics (body weight, waist and hip circumference, and bioelectrical impedance) | | X | | | | X |
| Brief Lifestyle Interview and non-quantified food record | X | | | | | |
| Contact and Demographic Information | X | | | | | |
| Food Taste Test | X | | | | | |
| Food Craving Inventory (FCI), Yale Food Addiction Survey (YFAS) , Liking and Wanting Procedure, Retrospective Visual Analogue Scales (RVAS) , Barratt Impulsiveness Scale, Delayed Discounting Task, and Food Familiarity and Liking Procedure | | X | | | | X |
| Urine Pregnancy Test | | X | | | | X |
| fMRI (fasting and fed state) | | X | | | | X |
| Randomization | | X | | | | |
| Study Product Dispensed | | X | X | X | X | |
| Adherence check/calculations (self-report and container return), provision of study foods | | | X | X | X | X |

Dose: The energy content of food provision in the SSB and solid groups will be 240 kcal/day. Participants are to consume 1 unit per day of the study.

Diet: Participants will receive no instructions for other dietary modifications; i.e., they will not be told to modify what or how much other food they consume.

Food Acceptability Form: Participants will be asked to rate the study foods for appearance, odor, flavor, texture, sweetness, and overall acceptability at screening. Each participant will be asked to circle the number from 1-9 for each of the characteristics after consuming the study foods.

Psychological Assessments:

Food Craving Inventory (FCI). The FCI^{9,10} is a 28-item measure of specific food craving. The FCI assesses the frequency with which an individual experiences a craving for a particular food. The measure consists of 4 empirically-derived factors: High fats, Sweets, Carbohydrates/starches, and Fast food fats. All items are scored in a 1 (Never) to 5 (Always) multiple choice format. The measure has been shown to be reliable and support has been found all aspects of validity.

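### Does asking habitual SSB drinkers to keep their usual intake contradict the no-dietary-modification rule and bias the liquid-versus-solid comparison?

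*Protocol*

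**What the plan says.** The request appears once, in the opening paragraph of the protocol's Inclusion and Exclusion Criteria: "Participants who consume SSBs will be asked to maintain their regular SSB consumption in addition to the SSB (or solid food". The sentence goes on to tie the product to the participant's random assignment, so it covers both arms.

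The general diet rule appears four times. The Background says: "There will be no instructions provided for any other dietary modifications". Specific Aims, the Diet paragraph under Procedures Involved, and Study Procedures all say: "Participants will receive no instructions for other dietary modifications". Each of these three then explains the rule: "they will not be told to modify what or how much other food they consume".

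The lifestyle exclusions remove people who "Consume more than seven 12 oz. sugar-sweetened beverages per week", so some lighter SSB drinkers will be enrolled.

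The Background gives the purpose as to "test if weight change is differentially affected by consumption of foods that are identical in carbohydrate (i.e. sugar) but vary in food form". It cites a commentary saying that "further research is needed to determine if people compensate differently over the long-term to energy consumed in solid vs. liquid form". The within-group hypothesis under Aim 2 is: "The SSB and solid groups will have increased weight compared to baseline (within group effects". Study Endpoints names feasibility and change in body weight as primary.

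**The concern.** Read quickly, the protocol seems to promise that nothing is said about the rest of the diet and then to say something about it to some participants. The subject makes this look worse. The Background is about whether people eat or drink less elsewhere when given liquid or solid sugar. For someone who already drinks soda, an obvious way to offset a supplied soda is to skip the usual one, and the request discourages exactly that.

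Two consequences would follow if this were a real fault. First, weight gain among SSB drinkers would be pushed in the direction of the within-group hypothesis. Second, if replacing drink with drink is more natural in the SSB arm than in the solid arm, the request would suppress a difference between the forms and favour the hypothesised absence of a between-group effect.

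The plan also has little to detect this with. Randomisation is stratified by sex and BMI class only, the model names age and sex, and the one scheduled diet record is non-quantified and taken at screening.

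**Working it through.** **Step 1: do the passages conflict?** The general rule does not exclude every dietary instruction. It excludes instructions for other dietary modifications, and three of its four statements explain this as not telling people to modify other intake. The SSB request asks people to maintain intake. Both can be followed together: staff tell no one to change anything, and they ask SSB drinkers not to change their SSBs. The request does go further than silence, so there is a tension, but neither statement breaks the other.

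**Step 2: how much energy does the request cover?** The protocol gives no figure for this, so there is none to reproduce.

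Inputs from the protocol: study SSB of 20 oz and 240 kcal, one per day (Background); entry limit of seven 12 oz SSBs per week, about one per day (lifestyle exclusions); Week 0 to Week 4, taken as 28 days (Study Timelines).

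Assumptions: habitual SSBs have the study drink's energy density; 7,700 kcal per kg of body weight, with a range of 7,000 to 9,000.

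- Energy density: 240 / 20 = 12 kcal/oz.
- One 12 oz SSB: 12 × 12 = 144 kcal.
- Share of the study dose at the entry limit: 144 / 240 = 60%. For non-drinkers it is 0%.
- Whole dose, no compensation: 240 × 28 = 6,720 kcal; 6,720 / 7,700 = 0.87 kg.
- Dose after full substitution at the limit: (240 − 144) × 28 = 2,688 kcal; 2,688 / 7,700 = 0.35 kg.
- Difference: 144 × 28 = 4,032 kcal; 4,032 / 7,700 = 0.52 kg (4,032 / 9,000 = 0.45 kg; 4,032 / 7,000 = 0.58 kg).

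**Step 3: what does 0.52 kg represent?** It is a ceiling for one person. It needs someone exactly at the entry limit who would have dropped every usual SSB without the request, who obeys the request fully, and who compensates through no other food. The last condition fits poorly with the Background, which cites a four-week study in which SSB consumers gained far less than expected without compensation.

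**Step 4: what could reach the trial averages?** The protocol gives neither the share of SSB drinkers nor their usual intake. Purely for illustration, suppose half the participants drink SSBs, at half the limit on average.

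- Within-group effect if all of them would have substituted fully: 0.52 × 0.5 × 0.5 = 0.13 kg.
- Between-arm effect if substitution would otherwise differ by 50 percentage points between arms: 0.52 × 0.5 × 0.5 × 0.5 = 0.065, about 0.07 kg.
- Between-arm effect if substitution would be equally common in both arms: 0 kg.

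The largest within-group value is 0.52 kg, if every participant sat at the limit and would have substituted fully. The smallest is 0 kg, if no one drank SSBs.

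**The case for a change.** The strongest case for acting is that the two regimens differ even though the sentences are compatible. A participant left entirely alone may drop a usual soda because one was supplied; a participant given the request is asked not to. The weight change being estimated is therefore slightly different. The request also sits only in the eligibility paragraph. Staff working from the Diet or Study Procedures text would not see it, so practice could vary. With 10 people per arm, SSB drinkers could be unevenly distributed by chance, and no scheduled measurement shows whether the request was followed. The pilot is also meant to supply data for powering a larger study.

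Part of this stands. The request does discourage one route of compensation for a subset of participants, and it is placed where staff delivering the intervention may not look. A cross-reference would be an editorial convenience.

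The rest does not carry. The request is the same in both arms, and nothing in the protocol shows that substitution would be commoner with the liquid product. Compensation through every other food remains open. The aims and endpoints concern weight change by food form; compensation is the motivation, and no aim or endpoint estimates it, so no stated conclusion is mislabelled. Tabulating habitual intake or adding a sensitivity covariate commonly belongs in the statistical analysis plan, which is not at hand. A further covariate would offer little with 20 participants and age and sex already in the model. A weekly SSB question would be extra data collection and would correct no wrong rule.

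**Conclusion.** No change follows. The apparent contradiction comes from reading the general rule as a ban on all dietary instruction, when it covers only instructions to modify other intake. What remains is a trade-off. Holding usual SSBs constant makes the 240 kcal/day a clean addition in both arms; leaving them free allows one more route of compensation. Either is a defensible design for comparing food forms, and this review does not choose between them.

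The energy at issue runs from 0 to 60% of the study dose per person. The individual ceiling is 0.52 kg over 28 days (0.45 to 0.58 kg across the assumed energy equivalents), and the illustrative between-arm effect is about 0.07 kg. These figures rest on the assumed energy density of habitual drinks, the assumed kcal per kg, and, for the averages, assumed shares of drinkers and substitution. A reader should take the weight results as the response to the study product with usual SSB intake held. That is how the eligibility section already describes the regimen, so the results can be interpreted without amending the protocol.
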